1. Visit 1: Informed consent process will be conducted at this visit. Assessments include best-corrected distance visual acuity (BCDVA, Snellen chart), manifest refraction, intraocular pressure (IOP), corneal topography (if astigmatism correction), eye dominance, slit lamp examination including dilated fundus exam, cataract density and type. Any testing that is part of the site's standard of care preoperative cataract surgery evaluation may be performed prior to the informed consent being signed provided these tests are conducted within 90 days of the surgery and notation of the date performed is entered onto the CRF. The surgeon's standard pre cataract surgery treatment will be used in all his patients

Each subject will be randomized to Group A (emmetropia OU) or B (mini monovision). Randomization will ensure that an equal number of subjects are enrolled in each group.

- Visit 2: The surgeon may use his preferred small incision cataract extraction technique (manual phacoemulsification or laser assisted). The assigned lens will be implanted in the bag. The following information will be captured the day of surgery: phaco technique (manual or laser), lens implanted and power, target refraction for IOL power implanted, additional surgical procedures, intraoperative complications, and any device deficiencies. The surgeon's standard post cataract surgery treatment will be used in all his patients. IOL power changes based on intraoperative aberrometry (i.e., ORA) are not allowed.
- 3. Visit 3: monocular UCVA (Snellen), slit lamp examination, IOP, and lens orientation (if toric lens and deem necessary by the investigator) and any device deficiencies.
- 4. Visit 4: Slit lamp examination, manifest refraction, monocular and binocular UCDVA, BCDVA, UCIVA (at 66 cm), DCIVA (at 66 cm), UCNVA (at 40 cm), and DCNVA (at 40), IOP, IOL orientation (if toric lens) and dilated fundus exam as deemed necessary by the investigator, patient satisfaction, visual symptoms and spectacle independence questionnaires, and any device deficiencies.

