5. STATISTICAL CONSIDERATIONS

A. Sample size

The sample size estimates depend in large part on the standard deviation (SD) for logMAR UCIVA. Assuming a SD of 0.12 (from a previous Eyhance study), for the two-sided t-test (alpha =0.05) for the intermediate visual acuity endpoint, we will need 31 subjects in each group (emmetropia / mini monovision) to detect differences of 0.1 logMAR (1 line difference) with 90% power. Total sample size = 62. Allowing 10 % for the potential confounding factor of having 2 sites, and 10% assumed dropout rate, 74 subjects will be enrolled (37 in each group). Table 2 summarizes the sample size estimate.

Table 2. Sample size estimate.

	TOTAL	Mini monovision	Emmetropia
Sample size	62	31	31
10% multiple sites	6	3	3

10% dropout rate	6	3	3
Total sample size	74	37	37

B. Statistical Analysis

All data will be collected by the site and entered into a database. Subjects will be assigned an ID number. Data analysis will be performed without patient identification. Statistical analysis will be performed using standard descriptive statistics and other tests as deemed appropriate based on the characteristics of the data to be analyzed. All statistical tests will be two-sided and interpreted at a 5% significance level. Comparisons between the groups will be made. Data analysis will be conducted by a third-party consultant.

C. Study Endpoints:

Comparisons between the groups:

1. Primary Endpoints:

Binocular distance-corrected intermediate (66 cm) visual acuity at 3 months. Distance corrected. DC, for the purpose of this study, is defined as corrected for the target refraction (i.e. emmetropia OU corrected for plano. Mini monovison dominant eye corrected for plano and the non-dominant eye for -0.75).

2. Secondary Endpoints:

- 1. Binocular defocus curve at 3 months
- 2. Binocular low contrast distance visual acuity at 3 months
- 3. Uncorrected and distance-corrected near (40 cm) visual acuity at 1 and 3 months
- 4. Uncorrected and distance-corrected intermediate (66 cm) visual acuity at 1 and 3 months
- 5. Uncorrected and best-corrected distance (4 m) visual acuity at 1 and 3 months
- 6. Distance-corrected near visual acuity at best distance at 3 months
- 7. To evaluate patient's overall satisfaction of their vision
- 8. To evaluate patient's spectacle independence
- 9. To evaluate visual symptoms using a questionnaire.
- 10. Residual mean spherical equivalent refraction at 3 months
- 11. Residual refractive sphere at 3 months

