- 12. Residual refractive cylinder at 3 months
- 13. Percentage of eyes with postoperative MRSE accuracy to target ≤ 0.5D at 3 months

D. Safety Analyses

The type, severity, duration and frequency of reported ocular adverse events will be tabulated for each group. Adverse events will also be summarized for events that were considered

[name] 10

treatment-related. Comparison of treatment groups with respect to the proportion of study patients reporting adverse events will be made using Fisher's Exact Test.

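### Secondary endpoint 13 compares refractive accuracy only as within or beyond 0.5 D of target; comparing absolute error in dioptres would use data already collected and usually give more power

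*Combined protocol and SAP*

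**What the plan says.** Section 5.C.2, item 13, is "Percentage of eyes with postoperative MRSE accuracy to target ≤ 0.5D at 3 months". The endpoint list stands under the heading "Comparisons between the groups", and section 5.B adds "All statistical tests will be two-sided and interpreted at a 5% significance level", so a between-group comparison is intended as well as a description. No test is named for item 13. Section 5.B allows descriptive statistics and "other tests as deemed appropriate based on the characteristics of the data to be analyzed". Nothing is said about handling two eyes per patient.

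Item 10 is "Residual mean spherical equivalent refraction at 3 months". Items 11 and 12 are residual sphere and cylinder. None of the three is stated relative to target.

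Both ingredients of a continuous accuracy measure are collected. Section 3.D, Visit 2, records the "target refraction for IOL power implanted", and manifest refraction is taken at Visit 5. Section 3.B sets the targets: plano for both eyes in Group A; plano for the dominant eye and -0.75 D for the non-dominant eye in Group B.

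**The concern.** Accuracy to target is a number for each eye, |Month 3 MRSE minus target| in dioptres. After the cut, an eye 0.55 D off counts the same as one 1.5 D off, and an eye exactly on target the same as one 0.45 D off. The plan cites no rule that requires the cut for the comparison.

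The arms differ only in refractive target. Whether each arm reached its target equally well therefore bears on how the uncorrected acuity, satisfaction and spectacle-independence results are read. If the test of accuracy is weak, a real loss of accuracy in one arm is more likely to be reported as no difference.

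**Working it through.** **1. The plan's own power figure.** Section 5.A covers intermediate acuity only: "we will need 31 subjects in each group (emmetropia / mini monovision) to detect differences of 0.1 logMAR (1 line difference) with 90% power". With SD 0.12, n = 2(1.960 + 1.282)² × 0.12² / 0.1² = 2 × 10.51 × 1.44 = 30.3, rounded up to 31. An exact t-test calculation gives 89.8% power at 31. The figure reproduces, but it says nothing about item 13: the plan gives no SD, expected percentage, effect or power for refractive accuracy.

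**2. Does another endpoint fill the gap?** Item 10 as written is raw residual MRSE. Averaged over a patient's eyes, the intended group difference is (0 + (-0.75))/2 = -0.375 D. Simulated at 33 per group and correlation 0.5, a test on it rejects about 87% to 99.9% of the time in the scenarios of step 4. It picks up the design, not accuracy.

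**3. Assumed inputs.**
- Patients: 37 per group less 10% dropout is 33.3, taken as 33.
- Errors from target: normal and centred on zero, two per patient, between-eye correlation 0.2 to 0.8.
- Tests: patient-level two-sided 5% t-tests on (a) the fraction of a patient's eyes within 0.5 D and (b) mean absolute error.
- For SD σ, the share within 0.5 D is 2Φ(0.5/σ) - 1 and the mean absolute error is σ√(2/π). For σ = 0.35 these are 84.7% and 0.279 D.

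**4. Scenarios with a clear difference in spread (correlation 0.5).**

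| Assumed SDs in the two arms (D) | Eyes within 0.5 D | Mean absolute error (D) | Power, cut | Power, absolute error | Gain (points) |
|---|---|---|---|---|---|
| 0.30 vs 0.40 | 90.4% vs 78.9% | 0.239 vs 0.319 | 41% | 48% | 7 |
| 0.35 vs 0.50 | 84.7% vs 68.3% | 0.279 vs 0.399 | 54% | 66% | 12 |
| 0.40 vs 0.60 | 78.9% vs 59.5% | 0.319 vs 0.479 | 62% | 78% | 16 |
| 0.45 vs 0.65 | 73.3% vs 55.8% | 0.359 vs 0.519 | 51% | 69% | 18 |
| 0.35, but 0.60 in Group B non-dominant eyes | 84.7% vs 72.1% | 0.279 vs 0.379 | 39% | 52% | 13 |

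In the last row, Group B averages its two eyes: (84.7 + 59.5)/2 = 72.1% and (0.279 + 0.479)/2 = 0.379 D. Over correlations 0.2 to 0.8 the gain is about 5 to 22 points. A rank test on absolute error gains about 0 to 14. Rounding errors to 0.125 D steps leaves about 5 to 16. With equal SDs of 0.35 D, type I error is 3.9% to 4.8% for the cut and 4.5% to 4.9% for absolute error.

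**5. Scenarios with a small difference or a shift (correlation 0.5, cut vs absolute error).**
- SD 0.35 vs 0.40 D: 12.8% vs 15.3%.
- SD 0.40 vs 0.45 D: 10.2% vs 12.4%.
- Mean shift 0.1 D, SD 0.35 D: 5.7% vs 6.1%.
- Mean shift 0.2 D, SD 0.35 D: 13.0% vs 15.5%. Signed error from target has about 75%.
- Shift of 0.2 D in Group B non-dominant eyes only: 6.8% vs 7.8%.

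The gain here is about 0 to 3 points. At a 0.3 D shift it is about 7 to 12, and signed error is again far stronger (98% against 51% for absolute error).

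**6. Wider assumptions.** Treating eyes as independent and allowing a reference SD of 0.25 to 0.50 D, the loss runs from about 0 to 29 points.

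**The case against.** Four objections have force.

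- **Size.** A reader might infer that the cut always costs 5 to 22 points. The documents do not support that. They give no SD for refractive error and no reason to expect spreads a third to a half apart when both arms receive the same lens models. Step 5 shows the loss nearly vanishing under other assumptions, and a rank test can gain nothing.
- **Item 10.** A reader might infer that item 10 has only about a 5% chance of flagging a difference. That figure belongs to signed error from target when only the spread differs. Item 10 as written rejects nearly always, by design. Its descriptive SDs would ordinarily show spread, but no comparison of accuracy follows from them.
- **Systematic miss.** Absolute error is weak against a shift, so it cannot stand alone. This stands, and it is why signed error belongs beside it.
- **Definition of target.** The recorded value for the implanted power may differ from plano or -0.75 D within the tolerances in section 3.B, and distance from the arm's nominal target arguably matters more for uncorrected acuity. The definition must therefore be stated.

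It is also true that item 13 is the last of 13 secondary endpoints, that no test is named for it, so the losses are measured against a test assumed here, and that absolute error could be added at analysis without new data.

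**Conclusion.** The point holds as a conditional one. Item 13 discards the size of each eye's error, the data to keep it are collected, and no other listed endpoint measures distance from target. The loss is about 5 to 22 points of power against a t-test on mean absolute error (about 0 to 14 with a rank test) under the assumptions of steps 3 and 4. It is about 0 to 3 points for small SD differences or shifts of 0.1 to 0.2 D.

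A reader might go further and infer that the main result or the sample size is compromised. The documents do not support that: the primary endpoint is measured with each eye corrected to its target refraction, the sample size rests on intermediate acuity, and no power is stated for item 13. Label: cheap improvement.

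**What to change.** In section 5.C.2, item 13:

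- Make the compared quantity |Month 3 MRSE minus target| in dioptres, stating that target is the value recorded at surgery for the implanted power.
- Average it over each patient's two eyes and compare groups at the patient level with a two-sided 5% t-test, giving the mean difference and its 95% CI.
- Add a rank or permutation check, because absolute errors are right-skewed.
- Report signed error from target alongside, to show any systematic miss.
- Keep the percentage of eyes within 0.5 D as a descriptive figure for each group.

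The cost is a sentence or two of text, with no new data, visits or patients. The small downside is that the tested result is in dioptres rather than the familiar percentage.

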6. DATA HANDLING AND RECORD KEEPING

A. Confidentiality

To ensure confidentiality in this study, records of the participants will be examined only by the principal investigator and research staff involved in the study. Study records will be kept on file at each site. Any statistical analysis and publication will not include any subject identifiers. Medical records will be made available only for review by the investigators, study Monitor or Auditor, Sponsor Company or Research Institution, the IRB, and other State or Federal Regulatory Agencies, if necessary. All information in these records will be kept confidential.

B. Records Retention

The PI is accountable for the integrity, retention and security of all study related data. The investigator must maintain accurate, complete and current records relating to the clinical study. The investigator must maintain the required records during the investigation and for a period of 3 year after the date on which the investigation is terminated or completed.

7. STUDY MONITORING, AUDITING, AND INSPECTING

The nature and location of all source documents will be identified to ensure that original data required to complete the case report forms (CRFs) exist and are accessible for verification by the monitor. If electronic source records are maintained, these records must be 21 CFR Part 11 compliant and will be printed and certified for verification by the monitor as needed.

Required examination must be recorded on the CRFs. Provided CRFs can be used as source document. All data reported must have corresponding entries in the source documents. The principal investigator or sub-investigator must review the reported data and certify that the CRFs are accurate and complete. No subject identifiers should be recorded on the CRFs beyond subject number, subject initials and study specific identifiers.

Data from CRFs will be entered into a database provided to each site, site will email the password protected file to the study manager with the CRFs for remote monitoring. Additionally, monitoring site visits will be made by the study manager throughout the study.

Upon completion of the CRFs, the data will be reviewed by study manager and statistician for accuracy and completeness. If corrections and/or any additions to the data are deemed

necessary, queries will be generated and forwarded to the investigative site. Designated research staff is expected to respond to data queries in a timely manner and ensure that the corrections and changes made to the data in the database are reflected in the subjects' source documentation. Any changes will need to be initialed and dated by the authorized personnel making such changes. Data will not be sold to third parties nor will it be used for future research.

Electronic data will be stored and accessed on a portable device. The laptop is password protected and only the study manager has access to it. Additionally, database will be password protected.

8. INVESTIGATIONAL PRODUCT

A. Description

The Eyhance IOLs (DIB00 and DIUxxx) are monofocal refractive IOLs designed to enhance intermediate distance vision without compromising distance vision. The lens power continuously increases from its edge to the center extending the range of vision when compared to a standard monofocal IOL.

B. Treatment/Dosing Regimen

The Tecnis Eyhance IOL is intended for primary implantation for the visual correction of aphakia secondary to removal of a cataractous lens in adult patients. The IOL will be implanted at time of uncomplicated routine cataract surgery. Intraocular lenses are implantable medical devices and are intended for long term use over the lifetime of the patient.

C. Method for Assigning Subjects to Treatment/Dosing Groups

Each site will be provided with randomization envelopes. The envelopes will be sequentially numbered.

D. Subject Compliance Monitoring

Since the IOL is implanted at time of cataract surgery, subject compliance will not be an issue in this particular study.

E. Packaging, Receiving, Storage, Dispensing and Return

An account will be set up with the manufacturer of the lens (Johnson and Johnson Vision) that will provide the lens at no cost to the participants. IOLs will be ordered once the subject's qualification for the study has been confirmed. IOLs will be shipped to the site and will be stored and dispensed following the routine standard of care for cataract surgery. Unused IOLs will be returned to Johnson and Johnson Vision following their instructions.

Or, Johnson and Johnson Vision will provide a consignment of lenses that will be stored at the site and unused IOLs will be returned to Johnson and Johnson Vision following their instructions at the

end of the study.

In both instances, an implantation log will be kept.

9. ETHICAL CONSIDERATION

This clinical trial will be conducted in accordance with the principles of the Declaration of Helsinki, and Good clinical practice. The Investigator and all clinical trial staff will conduct the clinical trial in compliance with this protocol. The Investigator will ensure that all personnel involved in the conduct of the clinical trial are qualified to perform their assigned duties through relevant education, training, and experience. Deviations from the clinical protocol must be documented in each subject's study records including the dates and reasons for each deviation. The PI must ensure that all aspects of the trial are in compliance with the applicable regulatory laws and conditions of approval imposed by the IRB.

10. RISKS AND BENEFITS

The risk of being in the study is not greater than the risk of undergoing routine cataract surgery with implantation of monofocal intraocular lenses. However, there is always the risk that uncommon or previously unknown side effects may occur. The study includes additional postoperative examinations at no cost.

11. IN CASE OF AN INJURY RELATED TO THIS RESEARCH STUDY

Every effort to prevent study-related injury will be taken by the study doctor and staff. In the event a patient is injured as a direct result of the study while following the study instructions and requirements, the patient will be instructed to immediately contact the principal investigator and/or study staff. Treatment will be provided as needed for those injuries caused directly by this research study. In the event of injury or illness caused by or occurring during the participation in this study, all charges for medical care provided will be billed to the patient's insurance company. The medical care costs for injuries or illnesses that are not caused directly by the research study will not be covered.

